15.5 Definition of Device Deficiency (DD)

Device deficiency (DD) is the inadequacy of a medical device related to its identity, quality, durability, reliability, safety or performance, such as malfunction, misuse or use error and inadequate labelling. All occurrences of Device Deficiencies must be reported to the Sponsor using a DD Reporting Form (blank DD reporting forms will be provided to the site in the ISF). All occurrences of DD should be recorded for study purposes.

15.6 Definition of an Unanticipated Serious Adverse Device Effect (USADE)

An Unanticipated Serious Adverse Device Effect (USADE) is a Serious Adverse Device Effect which by its nature, incidence, severity or outcome has not been identified in the current version of the risk analysis report for the device being tested. All USADEs should be reported to the Sponsor using an SAE/SADE Reporting Form (see section 15.10).

The only expected occurrence relating to the study procedure is discomfort from obtaining the nasopharyngeal swab. In a small number of cases, the participant may experience bleeding from the nostril. However, this will be the same as for the gold standard test procedure and discomfort is likely to only last for a few seconds. Emergency Department staff are well experienced in managing those who may experience nose bleeds.

15.7 Classification of Adverse Event Causality

The Investigator is required to provide their opinion as to the likely causality between the Logicore System IVDD and the SAE/SADE. The classification of the relationship is categorised as follows:

- 1) Unrelated
- 2) Unlikely to be related
- 3) Possibly related
- 4) Probably related
- 5) Definitely related.

15.8 Classification of Adverse Event Seriousness

The Investigator is required to classify the seriousness of the SAE/SADE using the CTCAE v5.0 for the most appropriate grading from 1 to 5, where 1 is less serious and 5 is more serious. It should be noted that the term 'seriousness' is not the same as 'severity'. An AE may be considered severe but could be of minor medical significance. An AE is only considered to be serious if it results in any of the points as listed in 15.2, such that an AE can be considered severe but not serious, and vice versa.

15.9 Classification of Adverse Event Severity

The Investigator is required to classify the severity of the SAE/SADE. The severity is related to the intensity of the event, usually classified as mild, moderate or severe. Further guidance as to the classification is as follows:

- Mild: The participant is aware of the event or symptom, but it is easily tolerated
- Moderate: The participant experiences sufficient discomfort to interfere with or reduce their usual level of activity
- Severe: The participant experiences significant impairment of functioning and is unable to carry out their usual activities and/or the participant's life is at risk.

15.10 Reporting Requirements for SAEs/SADEs

SAE/SADEs (including Unexpected Serious Adverse Device Effects; USADEs) must be reported to the Sponsor if they are deemed to be specifically related to the study procedures or the study investigative device. In such cases, the Investigator or designee must submit an initial SAE/SADE report to the Sponsor as soon as possible (within 24 hours of knowledge of the SAE/SADE taking place). A follow up form should be submitted to update the Sponsor as to further information within 7 days and as more information is available until the conclusion of the SAE/SADE. Blank SAE/SADE Reporting Forms will be provided to the site in the ISF. A new form should be used for each SAE/SADE and when providing follow up details.

The Sponsor must submit an initial report for each SAE/SADE to the MHRA and REC whether or not the Sponsor considers it to be related to the Logicore System IVDD. A follow up report for each incident should be submitted to the MHRA and REC to provide full details of the investigation and the outcome of the SAE/SADE.

The Common Terminology Criteria for Adverse Events (CTCAE) v5.0 will be used to determine the most appropriate medical term for the event, along with the seriousness grading.

16.0 ETHICS AND REGULATORY COMPLIANCE

All performance evaluation studies of an *in vitro* diagnostic device involving participants in an NHS setting require the following approvals to be in place before the study can be declared open to recruitment:

- Research Ethics Committee (REC) approval
- Health Research Authority (HRA) approval
- Local NHS Trust approval: agreement of costings using the National Contract Value Review (NCVR) and signed contract using the model Clinical Trial Agreement (mCTA).

In addition, the MHRA must be informed that the study is taking place.

16.1 Research Ethics Committee and HRA Approvals

The Sponsor will ensure REC/HRA approvals are in place prior to undertaking this clinical study. All correspondence with the REC will be retained in the Sponsor's Trial Master File (TMF) and the site's Investigator Site File (ISF).

16.2 MHRA Notification

Before the study can begin, the Sponsor will inform the MHRA of their intention to perform the clinical study. The MHRA will provide confirmation of receipt but is not required to produce a 'Letter of No Objection' for a performance evaluation of an *in vitro* diagnostic device. Therefore, there is no requirement for regulatory authority to proceed.

16.3 Protocol Amendments

If it becomes necessary to make any substantial changes to the protocol or associated documentation during the study (such as patient information sheets and informed consent forms), the Sponsor will submit a Notice of Substantial Amendment to the REC and local hospital Trust to gain approval for the amendment. All approvals must be obtained before the amendment can be implemented. The MHRA will be informed of the amendment for their information.

The only circumstance in which a substantial amendment may be initiated prior to the necessary approvals is when the change is necessary to eliminate an immediate risk to the participants (i.e. an Urgent Safety Measure). In this case, accrual of any new participants will be halted until all required approvals have been obtained.

If the amendment is not classified as substantial (i.e. it is non-substantial), the Sponsor will inform the REC, MHRA and local hospital Trust of the details for their records, but the formal approval process is not required.

Details of all substantial amendments will be immediately included in section 4.0 of this protocol accordingly. Details of non-substantial amendments will be added to section 4.0 if/when the next substantial amendment is required.

16.4 Study Documentation and Reporting

Copies of all correspondence with the REC and MHRA will be kept in the Investigator Site File (ISF) as well as the Trial Master File (TMF). The Chief Investigator will be responsible for submitting a Progress Report to the REC within 30 days of the study being opened. Furthermore, the Chief Investigator will submit an Annual Progress Report (APR) to the REC each year and an End of Study Report within a year of the study being completed. If the study is terminated prematurely for any reason, the Chief Investigator will inform the REC.

16.5 Data Protection

All site staff must comply with the requirements of the General Data Protection Regulation (GDPR), the Data Protection Act 2018 and Trust Policy with regards to the collection, storage, processing, transfer and disclosure of personal information and will uphold the core principles including collecting the minimum data to achieve the aims of the study, ensuring participants understand how their data will be used and maintaining accurate and secure records.

16.6 Participant Confidentiality

When a participant signs the consent form and is enrolled into the study, they will be assigned a unique 3-digit study identifying number, serving to de-identify and pseudonymise the individual. This number will be the only means by which the Sponsor can identifying the participants. The Sponsor will have no access to participant identifiable details.

The site will maintain a subject log, detailing individual participants and their corresponding study identifying numbers. The subject log will not be available to the Sponsor. However, the study monitor will need access to the subject log and the original signed consent forms during the monitoring process to ensure they are reviewing the correct participant's medical records for source data verification purposes. This will be explained to the participants during the consent process.

The subject log containing the link between individual participants and study identifying number will be securely stored in a separate location to the study data, in a password protected digital file. The log will only be available to members of the site study team and the study monitor. Thus, the site is the data custodian for any participant identifiable data and the Sponsor is the data custodian for all de-identified pseudonymised data for the purposes of the study.

Despite employing best practice to minimise the possibility of a breach of participant confidentiality, in the event of identifiable details being passed to anyone outwith the immediate members of the site ED research team, the person discovering the breach must inform the Sponsor of the details within 24 hours. The Sponsor must then determine whether the breach is a high risk to the rights and freedom of the individual/s involved and if so, inform the Information Commissioner's Office (ICO) within 72 hours of the breach being discovered. The individual/s must also be informed of the breach without undue delay. The Sponsor will maintain a log of all participant identifiable data breaches (both high and low risk) that occur during the study.

16.7 Patient and Public Involvement

There was no patient and public involvement in the course of developing the Logicore System *in vitro* diagnostic device for CE marking. It was felt that patients and the public became well versed with PCR testing during the COVID pandemic and understand the basic premise of nasal swabbing to detect pathogens. This process has become widely accepted by the general public.

Prior to undertaking this study however, a snapshot of public opinion was obtained from 22 patients in the ED at Addenbrooke's Hospital. The patients were asked 'If we had 2 devices that could test for a bug like COVID or Flu, but we didn't know which device was the best, would you let us take 2 nasal swabs instead of 1 so we could work out which is best?' The patients were also told the swabs would be taken simultaneously, one from each nostril. 91% (20 out of 22) of patients said 'Yes', they would let us take 2 swabs to work out which device was best. One patient said 'No' and one patient said 'Don't know'. This demonstrates a high level of support, albeit in a small sample of the population, for our study to be performed.

Furthermore, one of the aims of this study is to assess the acceptability of the new device to the participants and staff.

16.8 Peer Review

During the development of this study protocol, the Sponsor consulted with several Consultant Clinicians who are independent of Logilet (UK) Ltd, to ensure the study is designed to assess potential clinical benefit for patients and health economic benefit to the hospital NHS Trust. As there is no Investigational Medicinal Product or other therapeutic agent involved in the study, and little risk to study participants, a formal Data Monitoring Committee or Data Advisory Committee will not be convened. The Sponsor will review study data as it is accrued and will liaise with the site study team if there are any concerns about safety to determine whether it is necessary to halt the study prematurely.

16.9 Audits and Inspections

16.9.1 Protocol Compliance

Protocol deviations, non-compliances, or breaches are departures from the approved protocol. The ISF and participants' source documentation/medical records will be reviewed by the study monitor to assess protocol compliance and ensure the validity of the study data. If the monitor detects any deviation from the protocol, it will be brought

to the attention of, and discussed with, the Chief Investigator to determine the reason for the deviation and to mitigate against further occurrences. If possible, the deviation will be corrected. If it is not possible to correct the deviation, the Sponsor will decide whether the data is still suitable for inclusion or should be excluded from analysis.

Similarly, if a member of the site team realises an accidental protocol deviation has occurred, they should immediately notify the Chief Investigator and the Sponsor, providing details of what has happened and how it differs from the approved protocol. The Chief Investigator and Sponsor will discuss whether the deviation can be rectified in any way. If it is not possible to correct the error, the Sponsor will decide whether the data is still useful or whether it should be excluded from the analysis.

The study monitor will provide protocol re-training to relevant team members following a deviation as required. If a member of the study team continues to deviate from the requirements of the protocol despite attempts by the Sponsor to re-train the individual, the Sponsor may request a replacement person to deal with further study participants.

Each Protocol Deviation (PD) will be classed as minor or major by the Sponsor; a deviation will be considered major if the integrity of the study data is deemed to have been jeopardised in any way. Details of major deviations will be reported to the Research Ethics Committee.

In addition, any breaches of Good Clinical Practice (GCP) must be documented and brought to the attention of the Chief Investigator and Sponsor immediately (within 24 hours of detection).

Prospective, planned deviations or waivers to the protocol are not allowed under the UK clinical trial regulations and must not be used.

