13.5.3 Study Sample Collection and Testing Process

Study staff undertaking the sample collection will wear appropriate personal protective equipment (PPE) for the risk exposure at all times, in line with CUH local guidelines for Infection Prevention and Control. To eliminate potential differences in the samples being tested, two nasopharyngeal swabs will be collected simultaneously. One swab will be tested by the gold standard Cepheid multiplex POC test (i.e. standard of care diagnostic testing as required by CUH Trust IPC policy) and the other with the novel Logicore System multiplex POC device. The Logicore System swab will be tested using a specific Logicore System buffer which will be provided for use in a closed vial by the Sponsor. The testing of each specimen (Cepheid or Logicore) must begin within 20 minutes from the time of swab collection, according to the specimen processing guidelines. There is no need to store the swabs/buffer solutions on ice. These can remain at ambient temperature for storage.

The Cepheid POCT is done in the laboratories above the ED. The Logicore System (i.e. the Analytical Module into which the Respiratory Pathogen Panel cartridge is loaded for analysis and the portable Operation Module with display screen, into which the cartridge details and participant anonymised details are input) will be located in a secure clinical area within the ED, with controlled access.

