14.0 STATISTICAL ANALYSIS PLAN

14.1 Rationale

According to the Office of National Statistics report on the results of the 2021 Census⁷, the population of Cambridge is approximately 146,000 people. Of this population, around 75% classed their ethnicity as White (comprising the following categories: British, Irish, Roma, Gypsy or Irish Traveller, or Other) and around 15% are children aged 15 years or less. For this clinical study, it is expected approximately 20% of participants will be less than 16 years of age, and the majority of participants will be white Caucasian, providing a casemix with external validity in line with the demographics of the catchment area.

This prospective paired diagnostic accuracy and economic evaluation study is designed to assess the clinical performance and potential health system impact of a new molecular Point Of Care Test for respiratory infections in the Emergency Department (ED) setting. The new Logicore System testing device detects six key respiratory pathogens including four infections currently targeted by the current gold standard test (Cepheid); Influenza A (Flu A), Influenza B (Flu B), Respiratory Syncytial Virus (RSV) and SARS-CoV-2. The Logicore System device detects two additional pathogens not included in the established POCT; *Mycoplasma pneumoniae* (MP) and human adenovirus (HAdV).

During the winter season planned for this study, the overall positivity of the current POCT for respiratory disease is estimated at 30-50% of those selected by the respiratory criteria for the standard test (CUH personal communication). However, it is recognised that infections do not distribute evenly by age, or season, or time of the season. For example, RSV is more common in the very young or elderly and has peaks later in the winter months. Thus, the statistical approach to assessment requires us to estimate how many true positives per infection type* might be expected to achieve a sensitivity of 95% with a 10% margin of error, not just overall.

Also, during the winter season, disease type incidence will occur in runs and hence it is possible to inadvertently populate the whole study with one type of infection.

Logically our total sample size will need to be calculated on the lowest prevalence infection. As this is planned as an Intention To Treat study (ITT), i.e. including clinical benefits, then 10-15% extra samples would provide a reasonable margin of samples to allow for withdrawals and invalid samples.

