*Table showing impact of variable distribution of infection type on defining sample numbers (after CUH data)

Infection	Estimated Prevalence in	Number Needed for 19
	Winter Population	Positives
RSV	~15%	~127
Flu A	~10%	~190
Flu B	~5%	~380
SARS-CoV-2	~10%	~190

As the basis of this study is to determine sensitivity of the Logicore System testing device, rather than combined diagnostic performance across all four infections (rather than each one separately) then we need to apply this distribution imbalance to the way we calculate the minimum sample number to ensure at least achieving our sensitivity goal for each pathogen.

All eligible participants, i.e. those selected by the respiratory and inclusion criteria noted above with respiratory symptoms and a signed consent form, will be enrolled in the study. Using dual swabs, respiratory samples will be collected simultaneously for use in both new (Logicore System) and gold standard (Cepheid) tests to ensure comparability. This method will reduce the risk that differences in test outcomes are the result of inequitable sampling.

The aim also is to use the inclusion/exclusion criteria to recruit consecutive patients in the ED, suspected of the target condition to attempt to reduce spectrum bias. This real-world sample ensures external validity.

As this POCT occurs in a real time ITT setting, sample swabs will be handled consecutively within a few minutes to enter them into the POCT devices with no delay before and between test commencing. Both devices are expected to deliver a result with a similar elapsed time envelope. Hence commonly both tests will be running in parallel at any moment and model more closely the normal pathways of care in use.

This study is primarily aimed at validating the performance of a new POCT device (Logicore System) against an existing POCT device (Cepheid). This is the basis for this statistical plan rather than using a reference standard/composite diagnostic test e.g. PCR + Chest X-Ray.

Blinding the study will be difficult because of the situation of the study.

With regards to incorporation bias, the new test result will not influence the gold standard result.

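### Section 16.9.1 lets the sponsor exclude participants with deviations case by case, without stated criteria and with nothing to keep the decision independent of the test results

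*Protocol*

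**What the plan says.** Section 16.9.1 states the rule twice. For an uncorrectable deviation found by the monitor, "the Sponsor will decide whether the data is still suitable for inclusion or should be excluded from analysis". For one found by the site, "the Sponsor will decide whether the data is still useful or whether it should be excluded from the analysis". Suitability and usefulness are the only tests, and neither is defined. The grading is also the sponsor's: "Each Protocol Deviation (PD) will be classed as minor or major by the Sponsor". The grade is not tied to exclusion.

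Other sections show the sponsor's position:

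- It is the UK subsidiary of the device's manufacturer (7.2).
- It is custodian of all pseudonymised study data (16.6).
- On accruing data, 16.8 says "The Sponsor will review study data as it is accrued", and that "a formal Data Monitoring Committee or Data Advisory Committee will not be convened".
- It owns the raw data and performs the analysis (16.10).
- On masking, 14.1 says only "Blinding the study will be difficult because of the situation of the study".

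The primary row of the estimand table (14.6) lists three intercurrent events: an invalid swab or test, withdrawal before testing, and an indeterminate gold standard. Protocol deviation is not among them.

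**The concern.** The primary endpoint is estimated separately for each pathogen, and a Cepheid-positive, Logicore-negative pair counts as a false negative (section 11.0). If whoever decides on exclusion can know which pairs are false negatives, a deviating false negative can be dropped while a concordant pair with the same deviation is kept. Sensitivity then rises without any departure from the protocol. False positives can be treated the same way, which would affect specificity and PPV. The study sets out to show higher sensitivity for the sponsor's own device (9.1), so the exclusion rule should be visibly independent of the results.

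Deviations that could trigger the rule are foreseeable. Section 13.5.3 requires that "The testing of each specimen (Cepheid or Logicore) must begin within 20 minutes from the time of swab collection". The site starts with capacity for two cartridges at a time (7.2), each taking about 63 minutes (7.1), so a third participant within the hour could breach the limit.

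**Working it through.** **Inputs from the protocol.** Expected sensitivity P = 0.95, precision d = 0.10, Z = 1.96 (14.3.1). Total sample 400. Prevalence is about 5% for Flu B, 10% for Flu A and for SARS-CoV-2, and 15% for RSV (table in 14.1).

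**The plan's own figure.** n = Z²P(1−P)/d² = 1.96² × 0.95 × 0.05 / 0.10² = 18.25, rounded up to 19 positives per infection. N = 19/0.05 = 380, plus 20 = 400. This agrees with 14.3.1.

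**Expected positives in 400.** Flu B 400 × 0.05 = 20; Flu A and SARS-CoV-2 400 × 0.10 = 40 each; RSV 400 × 0.15 = 60.

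**Effect of exclusions.** Sensitivity is TP/(TP+FN). After dropping k false negatives it is TP/(TP+FN−k). Intervals are exact (Clopper-Pearson) 95%.

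Flu B, 20 positives, 18 detected:

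| Excluded | Sensitivity | 95% CI |
|---|---|---|
| 0 | 18/20 = 90.0% | 68.3–98.8% |
| 1 | 18/19 = 94.7% | 74.0–99.9% |
| 2 | 18/18 = 100% | 81.5–100% |

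If 19 of 20 are detected (95%), one exclusion gives 19/19 = 100%, a gain of 5.0 points, and no further gain is possible.

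The commoner pathogens need more exclusions for the same shift:

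- 40 positives: from 38/40 (95%), one exclusion adds 2.4 points and two add 5.0. From 36/40 (90%), it takes four to add 10.0.
- 60 positives: from 57/60 (95%), one adds 1.6 points and three add 5.0. From 54/60 (90%), it takes six to add 10.0.

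**How often there is something to drop.** At a true sensitivity of 95% and 20 positives, the chance of at least one false negative is 1 − 0.95²⁰ = 64%, and of at least two 26%. Each must also coincide with an uncorrectable deviation, and the protocol gives no deviation rate. Assume a rate r, independent of the test result. The chance of at least one deviating false negative is then 1 − (1 − 0.05r)²⁰:

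| Assumed r | Chance of at least one |
|---|---|
| 5% | 4.9% |
| 10% | 9.5% |
| 20% | 18.2% |

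For two or more at r = 10%, the chance is 0.45%. If late or mishandled specimens are more prone to false negatives, these figures rise.

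**The case against.** **Access to results is inferred.** A reader might infer that the sponsor will have both devices' results in front of it when it decides. No section says so, and 16.8 mentions safety as the purpose of the accruing-data review. Custody, ongoing review and the absence of planned blinding make access likely and leave it unrestricted, but the supportable statement is that nothing prevents it.

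**Intention to treat.** A reader might also see a contradiction with 14.1, "As this is planned as an Intention To Treat study (ITT". The documents do not support that reading. The study is not randomised, 14.1 uses the term loosely to mean including clinical benefits, and the same sentence allows 10–15% extra samples for withdrawals and invalid samples. The label never promised that everyone would be analysed. What remains is that the allowance and the estimand table name reasons for loss, and deviation is not one of them.

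**Existing checks.** Deviations found by the monitor are discussed with the Chief Investigator, those found by the site go to the Chief Investigator and the sponsor, major ones are reported to the Research Ethics Committee, and source records are open to audit (16.9.2). These checks help. But the sponsor sets the grade, exclusion does not depend on it, and the decision stays with the sponsor.

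**Matters for a separate SAP.** Masked review and analysis sets are commonly defined there, and their absence here is not the point. The point is the discretion that 16.9.1 does state, which would conflict with a stricter SAP.

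**Frequency.** It would be too strong to say that deviations will be common. No rate is given, 14.1 expects loading within a few minutes, and the data list in 11.0 has swab and result times but no test start time, so late loading may not be recorded uniformly.

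**Conclusion.** The concern holds as a defect in a stated rule: 16.9.1 permits result-dependent exclusion from the primary analysis. It does not show that such exclusion is intended or likely. A shift of about 5 to 10 points from one or two exclusions applies only at the roughly 20 positives expected for Flu B. The upper end needs an observed sensitivity near 90%; at an observed 95% the most that can be gained is about 5 points. A reader might apply that range to every pathogen, but at 40 positives it takes about 2 to 4 exclusions and at 60 about 3 to 6. All of this assumes the tabled prevalences and that each dropped false negative also had an uncorrectable deviation. The point should be fixed. The unknown deviation rate and the existing checks keep it short of a defect that must be cured before the study can proceed.

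**What to change.** Replace both sentences in 16.9.1 with a rule that says:

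1. The primary analysis keeps all consented, eligible participants with valid paired results, except for a short list of exclusions fixed in advance. Examples are specimen misidentification, no valid consent, or consent withdrawn with destruction of the research sample requested under 13.3.
2. Deviations are classified from a listing with both devices' results removed, before database lock.
3. Every exclusion is reported with its reason, and a sensitivity analysis omits participants with major deviations.

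The list in item 1 is needed because keeping every valid pair whatever the deviation would retain misidentified specimens and participants without valid consent, and would conflict with 13.3.

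The cost is protocol wording and one masked listing. The small downside is that some imperfectly handled specimens stay in the primary estimate; the sensitivity analysis shows how far those with major deviations affect it.
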